3. Fuse CART digital biomarker data and I-CONNECT language markers to further boost the model screening performance.

III. Background

In recognition of the COVID-19 public health threat, Oregon Health & Science University suspended all in-person, *nonessential research on human subjects* on March 15th, 2020. The governor of Oregon went on to issue a stay-at-home order shortly thereafter. These restrictions lifted enough to permit remote trial

conduct and contactless materials delivery to subjects by June 8th. However, given the ongoing pandemic and uncertainty around possibly future COVID-19 restrictions, as well as the high-risk nature of our subject population (adults age 75 and older), it became necessary to adapt the protocol for remote conduct.

IV. Study Design

This study is a two-arm randomized controlled trial.

Participants will be randomized in a 1:1 ratio to the experimental or control conditions balancing the following factors:

- Cognitive status (healthy normal vs. MCI)
- Age (age 75-79 vs. age 80-84 vs. over 85+)
- Education (high school completion vs. below high school education)
- Sex (male vs. female)
- Mean Montreal Cognitive Assessment (MoCA)

Subjects will complete in-home assessments at the 6-month time point. All subjects will receive a follow-up telephone call approximately one month after the intervention period concludes. Subject participation in the study will last approximately seven months including the screening and follow-up period. In total, there are approximately four scheduled assessment calls (if assessment time points are split into multiple calls), plus additional technology troubleshooting calls, depending on group allocation.

A. Intervention Group

Half of participants will be randomized to the experimental group, the study intervention group. These subjects will engage in video chat conversations with study staff using an online video communication platform. Each video chat session will be 30 minutes long. Subjects will also receive a weekly telephone call, lasting approximately 10-15 minutes, to assess health and social activities.

The intervention period will last 24 weeks. Subjects in the intervention group will receive four chats per week (a high dose of the video chat intervention) for 24 weeks. The video chat frequency will then taper to a decreased dose of two chats per week during weeks 25 and 26 of the follow-up period.

B. Control Group

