Randomization to the control group or intervention group will occur prior to the Baseline visit, but subjects should not be notified of their group assignment until after the Baseline visit to help prevent the subjects from inadvertently unblinding the assessment staff.

If subjects are randomized but then withdraw and do not complete the Baseline visit, they will be removed from the randomization program to ensure study arms remain balanced. These subjects will be classified as drop-outs prior to randomization, as they are not informed of their group assignment.

If cohabitating subjects enroll in the trial, forced randomized will be used to assign the subjects to the

same study condition.

H. Intervention Period

The 24-week intervention period will begin once the Baseline procedures are complete. The intervention period will always start on a Monday.

For all subjects, Week 1 of the intervention period will start no more than two Mondays after the last Baseline-period procedure (the Baseline assessment or the technology installation, as applicable).

If a subject's Week 1 Day 1 is delayed more than 6 months from the date of their Screening visit, the subject will be rescreened. See section VI. E. Eligibility for rescreening details. Screening and Baseline data will be recollected.

1. Video Chat Intervention *Week 1 through Week 24*

The study intervention consists of structured 30-minute video chats between participants and study staff. Video chats will be conducted remotely using an online audio and video communication platform and a video chat device installed in the subject's home. The video chats will be audio and video recorded.

Novel conversation stimuli are provided for each chat, focusing on a theme with three possible topics and corresponding photos, to be visually presented to the participant during the chat via the video chat device. Stimuli include questions targeting three domains of cognition: episodic memory, semantic memory, and executive function. Stimuli will be used to initiate each chat, however subjects may direct the conversation as they find interesting or engaging. Study staff will attempt to maintain a neutral or positive chat tone.

The full chat intervention will last for 24 weeks. Chats will occur four days per week.

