All electronic data, including recordings of video chats, will be stored indefinitely on secure, password-protected OHSU servers, OHSU Box, and/or OHSU REDCap. All data will be coded prior to sharing. De-identified datasets are easily exported from OHSU REDCap though the recordings contain voiceprints, images of participants, and content that may identify the participant and therefore cannot be deidentified. Paper-based data collection forms will be destroyed after they have been digitized per the paper data handling process described in this protocol. Upon study closure, sites will send the signed consent forms, compensation paperwork, and other remaining paper source documents to OHSU via a courier service with tracking number and signature required for delivery. All signed paper-based consent forms will be stored in locked locations at OHSU for at least three years after study closure.

Separate IRB approval will be required for each human subject research project using identifiable data from the repository. Investigators wishing to obtain data from the repository for research beyond the specific aims of the original study may contact the repository Guardian and Principal Investigator, [name]. [name] will ensure that data are released according to OHSU policy and this protocol. A repository sharing agreement will be used each time data are released for research purposes. All signed agreements will be electronically kept on file indefinitely on a secure storage server. [name] will ensure the security and confidentiality of data and specimens during both storage and transfer. She will maintain a secure list of participants who withdraw their consent, and she will ensure no future use or sharing of their data. [name] will track data releases to be reported at annual IRB Continuing Review.

VIII. Data Analysis

The data analysis approach for this Remote Protocol remains as described in the main I-CONNECT study protocol. Data for the subset of subjects anticipated to enroll under this protocol (N=40) will be included in analyses as appropriate; this subset of subjects will not have data required for certain planned analyses, such as MRI data, and will therefore be excluded where necessary.

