Psychological well-being and person-specific levels of social interaction (i.e., changes in social engagement measured with the I-CONNECT Weekly Questionnaire administered weekly via telephone) will be monitored and controlled in the analyses along with other relevant variables, including APOE 4 status.

Video chats will be recorded and analyzed to determine longitudinal changes in speech patterns.

A. Analyses for Primary Outcomes

MoCA test scores (global cognitive function) are our primary outcome.

Secondary outcomes include: neuropsychological test results in the area of language-based executive function, measured by the T-Cog category fluency test (animals), and memory domains measured by

two T-Cog episodic memory tests (Craft Story Immediate and Delayed Recall). We will allocate a type I error rate of 0.05 for our primary outcome. The results will be cross-validated with NIH Toolbox cognitive batteries as exploratory analyses for those who had NIH Toolbox cognitive assessments. Potential mediation variables include the Psychological Well-Being portion of the NIH Toolbox. If Psychological Well-Being shows significant improvement in the experimental group compared to the control group over 6 months (in univariate analysis using $p < 0.05$), the measurement(s) will be examined as potential mediation factors in statistical models as secondary analyses. The Psychological Well-Being portion of the NIH Toolbox consists of 3 measurements: Positive Affect, Life Satisfaction, and Meaning and Purpose. The questionnaire and references for these scales are detailed in: <http://www.nihtoolbox.org/WhatAndWhy/Emotion/PsychologicalWell-Being/Pages/default.aspx>.

B. Sample Size Estimate

Our previous pilot study (based on a six-week intervention) showed Cohen's $d=0.53$ when comparing pre-post changes in language-based executive functions (Clinical Dementia Rating 0 and 0.5 groups combined) in the control and experimental arms. The sample size ($n=72$ completers for each group) in this trial provides 80% power to detect this difference at $\alpha=0.025$, using a two-tailed test (i.e., total type I error rate= 0.025), based on simulation results using non-pooled standard deviation (SD).

Two separate hypotheses are proposed. Stage I examines the efficacy of the high dose and Stage II examines the efficacy of the maintenance dose. Participants covered under the current protocol will be included into the high dose analysis

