Changes in primary and secondary outcomes between the control and experimental groups will be examined for the efficacy of high dose (month 0 – month 6, Stage I) and maintenance dose (month 6 – month 12, Stage II) using the Mixed-Effect Model Repeated Measure (MMRM) model under ITT. We will conduct per protocol analysis using those who completed at least 80% of targeted conversational sessions (experimental group) and the number of telephone check-ins (control group). The subjects recruited or in trial under the current remote trial protocol will be included where appropriate (i.e., high dose analysis).

Changes in primary and secondary outcomes between the control and experimental groups will be examined for the efficacy of high dose (month 0 – month 6, Stage I) and maintenance dose (month 6 – month 12, Stage II) using the Mixed-Effect Model Repeated Measure (MMRM) model under ITT. We will conduct per protocol analysis using those who completed at least 80% of targeted conversational sessions (experimental group) and the number of telephone check-ins (control group).

Changes in primary and secondary outcomes between the control and experimental groups will be examined for the efficacy of high dose (month 0 – month 6, Stage I) and maintenance dose (month 6 – month 12, Stage II) using the Mixed-Effect Model Repeated Measure (MMRM) model under ITT. We will conduct per protocol analysis using those who completed at least 80% of targeted conversational sessions (experimental group) and the number of telephone check-ins (control group).

[figure not shown]

Figure 1. Trial Dose Stages: Sample size for one group (MCI or normal cognition; both groups have the same planned sample size)

Changes in primary and secondary outcomes between the control and experimental groups will be examined for the efficacy of the high dose (Baseline-Month 6, Stage I) and the maintenance dose (Month 6-Month 12, Stage II) using the Mixed-Effect Model Repeated Measure (MMRM) model under intention-to-treat (ITT). We will conduct per-protocol analysis using those who completed at least 80% of the targeted conversational sessions (experimental group) and telephone check-ins (control group).

C. Analyses proposed for the New Aim 4

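### Cohabiting subjects are assigned to the same arm, but the efficacy model and sample size make no provision for within-household correlation; the effect on the standard errors is probably small and is easily allowed for.

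*Combined protocol and SAP*

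**What the plan says.** Section IV sets out individual allocation: "Participants will be randomized in a 1:1 ratio to the experimental or control conditions balancing the following factors". Section VI.G makes an exception: "If cohabitating subjects enroll in the trial, forced randomized will be used to assign the subjects to the" same condition. The second member of a pair therefore has no separate randomisation.

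Section VIII.B gives the efficacy model four times, three times as "using the Mixed-Effect Model Repeated Measure (MMRM) model under ITT" and once with the abbreviation spelt out. None of the four mentions a household term, a clustered variance, the covariance structure or a one-member-per-household analysis. The sample size paragraph in the same section has no design effect: "The sample size ($n=72$ completers for each group) in this trial".

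Section VIII opens by deferring to another document: "The data analysis approach for this Remote Protocol remains as described in the main I-CONNECT study protocol". That main protocol is not among the documents supplied. Nothing here gives an observed or expected number of cohabiting pairs.

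**The concern.** Eligibility (section V.B) requires one of three isolation criteria and does not require living alone, so two eligible people can share a home, and the protocol has a rule for that case. They share surroundings and routine and, in the experimental arm, have chats delivered through equipment in the same home. If their cognitive changes tend to move together, two subjects in the same arm carry less information than two independent ones.

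A standard MMRM models correlation between repeated measures on one person and takes different people as independent. Fitted that way, it would give intervals that are somewhat too narrow and a type I error somewhat above nominal. A result close to the significance threshold could then depend on a choice that the plan has not made in advance.

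**Working it through.** **1. The plan's own figure.** Inputs from section VIII.B: d = 0.53, 72 completers per group (read as per arm), two-tailed alpha 0.025, stated power 80%. The noncentrality is 0.53 × √(72/2) = 0.53 × 6 = 3.18. The noncentral t gives 81.9% power, and a simulation with unpooled SDs (100,000 runs) also gives 81.9%. The stated 80% is thus reproduced to within 2 points with independent subjects and no allowance for clustering.

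**2. Variance with same-arm pairs.** Take an arm of n subjects with m pairs, and let ICC be the correlation of six-month change within a pair. The variance of the arm mean is

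(σ²/n²)(n + 2m × ICC) = (σ²/n)(1 + f × ICC), with f = 2m/n the share of subjects in pairs.

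With the same f in both arms, the treatment contrast has the same inflation, VI = 1 + f × ICC. The correct SE is √VI times the independence SE, and the true size of a nominal 5% test is 2 × (1 − Φ(1.96/√VI)).

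**3. Range.** Both f and ICC are assumptions, since the documents give neither.

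| f | ICC | VI | √VI | 1.96/√VI | True size |
|---|---|---|---|---|---|
| 5% | 0.2 | 1.010 | 1.005 | 1.950 | 5.1% |
| 10% | 0.3 | 1.030 | 1.015 | 1.931 | 5.35% |
| 20% | 0.4 | 1.080 | 1.039 | 1.886 | 5.9% |

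The correct SE is thus 0.5% to 3.9% larger than the independence SE. Simulation with 72 per arm agrees: 4 pairs per arm at ICC 0.3 gives 5.4%, and 7 pairs per arm (f = 14/72 = 19.4%) at ICC 0.3 gives 5.6%.

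**4. Remote subjects only.** Section V.A expects about 40 enrolments under this protocol. If 8 of them (20%, assumed) are in pairs among 2 × 72 = 144 completers, f = 8/144 = 5.6%. ICC 0.2 gives VI = 1.011 and size 5.13%; ICC 0.4 gives VI = 1.022 and size 5.26%. The correct SE is 0.6% to 1.1% larger.

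**5. Power at 72 per arm, alpha 0.025, with clustering allowed for.** It is 80.6% at f = 10% and ICC 0.3, and 79.3% at f = 20% and ICC 0.3, against 81.9% with no clustering.

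**6. When the effect vanishes or reverses.** With f = 0 or ICC = 0 there is no inflation. At f = 10% and ICC = −0.1 the size is 4.9%.

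**The case against.** A reader might infer that the model treats all subjects as independent and that type I error is therefore inflated for the primary and every secondary outcome. The documents do not support this, for four reasons.

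- Independence is inferred from silence. The plan gives only a model name and defers the analysis to a main protocol that may deal with households. This stands. However, section VIII restates the outcomes, the model and the analysis sets, and a reader would look there for the handling of pairs.
- The same-arm rule is shown only in the Remote Protocol, whereas section II bases the primary MoCA analysis on the pre-pandemic cohort alone. Whether that cohort was randomised under the same rule cannot be seen here. This stands and limits the point.
- The rule is conditional. No pair is documented, and both members would have to be aged 75 or over, socially isolated and otherwise eligible. What matters is also the correlation of change, which shared surroundings support less clearly than correlation of level. This stands: positive correlation is plausible, not established.
- For the secondary outcomes there is no allocated error rate to exceed. Section VIII.A says "We will allocate a type I error rate of 0.05 for our primary outcome", and the 0.025 appears only in the sample size paragraph. This stands.

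It can also be said that an effect of this size would hardly alter a conclusion. That is probably true, but it does not justify leaving the handling open, because a choice made after the results are known is harder to defend.

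**Conclusion.** The point holds in a limited form. The protocol creates household-level allocation for cohabiting subjects, and the analysis and sample size given here do not provide for it. A standard MMRM would slightly understate the standard errors, on two conditions that the documents do not settle: that pairs enrol, and that their six-month changes are positively correlated.

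On the supplied text this affects the secondary outcomes and the all-randomised MoCA sensitivity analysis, through the remote subjects. The primary analysis is affected only if the main protocol has the same rule. The true size of a nominal 5% test is about 5.1-5.3% under the remote-only assumption and about 5.1-5.9% over the wider assumed range. The upper end needs about 7 pairs per arm of 72, for which the documents give no support. This is a low-cost correction with a small expected effect, and no evidence that any result of the trial is wrong.

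**What to change.** Add to section VIII.B that the efficacy models use household-clustered (cluster-robust) standard errors, with single-person households as clusters of one, and that the number of households and of cohabiting pairs is reported per arm. If the main protocol has the same assignment rule, the sentence should cover the primary analysis too; if it already specifies the handling, a cross-reference is enough.

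A household effect on the change score is an acceptable alternative. A time-constant household random intercept is not, if baseline is modelled as a response: it enters baseline and Month 6 equally, cancels from each subject's change, and leaves the SE of the treatment contrast in change uncorrected.

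The cost is one sentence and a household identifier in the analysis dataset. Clusters stay numerous: even with 7 pairs per arm there are 72 − 7 = 65 households per arm. Intervals may become slightly wider. If no pairs enrolled, the report of households per arm will show it and the issue falls away.
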